An advanced doctoral student or a doctoral level member of the study staff will obtain written informed consent, and will thoroughly review the consent form with the potential participant. If an advanced doctoral student obtains consent, a licensed physician investigator will be available to speak with the subject during the consent process. Subjects who are consented by advanced doctoral students will be offered the option of speaking with a physician Investigator during the consent process and this will be recorded in research records. During the consenting process, potential participants will be apprised of the voluntary nature of their participation in the study and that they can withdraw at any point in the study without penalty. Specifically, we will reassure all potential participants that refusal to participate will in no way influence their care or affiliation with the Clinics at the Massachusetts General Hospital or any other Harvard Medical School affiliated hospital. Potential participants will be informed that the study will examine how oxytocin impacts their performance on different social cognitive tasks, but they will not be informed as to the exact study hypotheses (e.g., how oxytocin's effects on social and cognitive functioning may relate to their BDD symptoms). It will be necessary to use incomplete disclosure at the outset of the study to ensure maximum internal validity of study results. Potential participants will also be given as much time as needed to consider participation, and will be given an opportunity to ask questions about the study prior to signing the consent form. We will obtain written informed signed consent through the use of a PHRC approved written consent from all participants before they enter into the study and start study procedures. After signing the consent form, participants will be given a copy of the consent, and the original copy will be filed in a locked file separate from study data in a research office.

[figure not shown]
Treatment Assignment Procedures:

Given the cross-over design, all participants will receive an oxytocin and placebo nasal spray at two separate visits. The MGH Research Pharmacy will randomize the order of nasal sprays that will be given to participants, and will thus be un-blinded of assigned drug condition for participants' study visits. All other study staff, as well as participants themselves, will be blind to drug condition.

V. Study Procedures

Overview of Study Procedure:

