The study will consist of 3 study visits in total. The first visit will involve the diagnostic assessment and medical screen to determine eligibility for the study, in addition to the administration of clinician-administered and self-report questionnaires. This visit will take approximately 2.5 hours to complete. If participants are eligible, they will be asked to return to the clinic for two additional study visits, which will be identical in procedure and take approximately 2 hours each to complete. Female participants must complete Visits 2 and 3 during the active phase of their contraceptive medication (e.g. not during their menses); female subjects using multiphasic contraceptives must be on the same dose of ethinyl estradiol for both Visit 2 and 3. Participants will be instructed to avoid alcohol, caffeine, and nicotine for 24 hours prior to Visits 2 and 3. These visits will involve the administration of both an oxytocin and placebo nasal spray, in randomized order, and the completion of various social cognition tasks. They will be separated by a one-week washout period (**maximum 28 day** window period). The study design and procedures are represented in the following schematic:

[figure not shown]
Diagnostic Assessment and Medical Screen:

After obtaining informed consent, participants will be administered the Structured Clinical Interview for DSM-IV (SCID-I/P; First, Spitzer, Gibbon, & Williams, 2002) to determine diagnostic eligibility. The SCID allows the investigator to assess all diagnostic inclusion and exclusion criteria. Participants who are recruited for the healthy control

group will be given the SCID-I/P to confirm the absence of Axis I psychopathology. Participants who meet the diagnostic inclusion and exclusion criteria will be given a medical screen consisting of a history and physical examination (H&P) by a study nurse or physician to determine the participant's eligibility and safety for the study. In addition, a urine pregnancy test will be given to females during this visit, as well as at the beginning of Visits 2 and 3 to ensure continued eligibility.

Investigational Agent (dose, method, schedule of administration, dose modifications):

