Mini-Markers Scale (MM; Saucier, 1994): The Mini-Markers Scale is a 40-item self-report measure of the five factor model personality factors: extraversion, agreeableness, conscientiousness, emotional stability, and openness. It asks participants to rate how accurately each item describes themselves on a 1-9 point Likert scale ranging from "extremely inaccurate" to "extremely accurate."

Adverse Events Form: This self-report form will be administered at Visits 2 and 3 after nasal spray administration to assess for any adverse events. Participants will be asked to report on a symptom checklist whether they experienced a negative reaction to the oxytocin and placebo nasal sprays. If participants endorse 'yes' on any item, a study clinician or nurse will follow up and ask them whether the symptom resolves by the end of the study visit.

Assessment of Blind Form: This questionnaire will be given at Visits 2 and 3 after nasal spray administration to assess for participants' expectancies regarding the drug they received. Participants will be asked which nasal spray they believe they received (oxytocin or placebo), to rate their degree of certainty, and to describe their reasons why.

Tasks:

The following tasks will be administered at each study visit approximately 45 minutes after drug administration. The order of tasks will be the same within each participant in the study between Visit 2 and Visit 3 in order to minimize variance for the within-subject analysis and isolate the effect of the drug. However, the order of tasks will be counterbalanced between participants in the study, to account for possible carry-over effects.

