Prior to analysis, all major variables will be screened for inconsistent or abnormal values, and continuous measures assessed for skewness and outliers. Variable distributions will be examined and transformations made when distributions are skewed or otherwise violate analytic assumptions. Linear regression models will be used, and in all models, the effect of diagnosis will be based not on the global (type III) effect, but on the specific pair-wise comparison of interest: BDD vs. Healthy Controls. Analyses will be conducted using SAS v9.4 (SAS Institute, Cary, NC), and all models will employ a two-sided alpha=0.05 to determine significance.

Aim 1 Analyses:

The primary outcomes will be the Emotion Recognition Task total score and the Trust Game "back transfer" amount. Two sets of outcome scores will be obtained for each subject - one during placebo and the other during oxytocin administration. To test Hypothesis 1a, we will regress placebo outcome scores against diagnosis. To test Hypothesis 1b, we will regress oxytocin outcome scores against diagnosis, and will control for the placebo outcome score. If we find significant differences in oxytocin Emotion Recognition Task total score by diagnosis, we will further examine the 3 Emotion Recognition Task valence categories (positive, negative, neutral) as exploratory outcomes.

Aim 2 Analyses:

Secondary outcomes include the Posner Task difference score for disengagement response latencies between disgust vs. neutral faces, and the Interpretation Questionnaire total score. Mirroring the analyses for the primary aim, we will test Hypothesis 2a by regressing the placebo secondary outcome scores against diagnosis, and will test Hypothesis 2b by regressing the oxytocin secondary outcome scores against diagnosis, controlling for the placebo secondary outcome scores.

Exploratory Analyses:

Exploratory moderators include the BDD-YBOCS total score, YBOCS total score, LSAS total score, BFNE total score, ECR Anxiety subscale mean, ECR Avoidance subscale mean, and IPSM total score. To test the moderation effects, we will enter each moderator (one at a time) into each of the aforementioned linear regression models along with a covariate representing the interaction between the moderator and diagnosis (the term of interest). We will examine moderation of each pair-wise comparison separately.

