For all analyses, we will include concomitant medication use as a covariate, in order to control for the effect of concomitant medications on study results. We will also compare participants who are taking psychotropic medications from participants who are not, on

demographic and clinical variables, to ensure there are no systematic differences between these groups.

Power and Sample Size:

Given the novelty of our approach, no background data on the effects of oxytocin in BDD exist to inform the power calculation. Therefore, the proposed sample size of 40 participants (20 per group) was chosen based on feasibility. With 20 participants per group and a two-sided alpha=0.05, for our primary pair-wise comparison (BDD vs. healthy controls) of the mean within-subject difference (oxytocin vs. placebo) in Emotion Recognition Task total score and Trust Game "back transfer" amount, we will have 81% power to detect a moderate effect size of $f=0.23$.

VII. Risks and Discomforts

Oxytocin-Related Risks and Side Effects:

Between 1990 and 2010, there have been 38 controlled studies involving intranasal delivery of oxytocin (MacDonald et al., 2011). A total of 1,529 participants have received intranasal oxytocin or placebo, and nine studies have included participants (N=182) who had a developmental, medical, or mental health disorder. The dosage of oxytocin has typically been a single dose ranging from 20 international units (IU) to 40 IU. Out of the 1,529 participants who have received intranasal oxytocin or placebo, 279 (18%) reported mild side-effects (MacDonald et al., 2011). The most common side-effect was a feeling of calmness, but this did not differ between those who received oxytocin or placebo. A recent review of studies using intranasal oxytocin supported the short-term use of oxytocin, demonstrating that oxytocin produced minimal side-effects, no detectable differences in side-effects between oxytocin or placebo recipients, no subjective changes in recipients, and is equally safe to use with vulnerable populations as with healthy adults (MacDonald et al., 2011). The proposed study intends to use a single 24 IU dose of intranasal oxytocin, which has been the most commonly used dose in previous trials (25 out of 38 studies).

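### Neither visit period nor the randomised spray order is in any planned model, so a score shift between the two task visits would cost the Hypothesis 1b and 2b tests precision

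*Combined protocol and SAP*

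**What the plan says.** Section IV, Treatment Assignment Procedures, describes a cross-over: "The MGH Research Pharmacy will randomize the order of nasal sprays that will be given to participants". Section V, Overview of Study Procedure, has eligible participants return for "two additional study visits, which will be identical in procedure", separated by a one-week washout with a 28-day maximum. No stratification or blocking of order by diagnosis is described.

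Section VI gives the models:

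- Hypotheses 1a and 2a: placebo score on diagnosis.
- Hypothesis 1b: "To test Hypothesis 1b, we will regress oxytocin outcome scores against diagnosis, and will control for the placebo outcome score".
- Hypothesis 2b: the plan "will test Hypothesis 2b by regressing the oxytocin secondary outcome scores against diagnosis, controlling for the placebo secondary outcome scores".
- Exploratory: the same models plus one moderator and its interaction with diagnosis.
- Throughout: "For all analyses, we will include concomitant medication use as a covariate".

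Visit, period, sequence and spray order appear in none of them. Section V, Tasks, keeps each participant's task order the same at both visits to "minimize variance for the within-subject analysis and isolate the effect of the drug", and counterbalances task order between participants. That concerns the order of tasks within a visit, not which spray came first.

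**The concern.** Every participant does the same tasks twice. If performance changes from the first task visit to the second, the change falls on the oxytocin score for those given placebo first and on the placebo score for those given oxytocin first. The placebo covariate does not absorb this. The shift moves outcome and covariate in opposite directions across the two orders, so it adds residual variance and weakens the covariate. The washout deals with residual drug, not familiarity. Fixed task order cannot remove a difference between visits.

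A shift is most plausible for the Emotion Recognition total, a primary outcome scored on correct answers. It is less clear for three outcomes:

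- the Posner difference score, where general speeding largely cancels;
- the Interpretation Questionnaire, which has no correct answer;
- the Trust Game back-transfer amount, which is returned by study staff.

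What is at stake is mainly precision in a small trial: "the proposed sample size of 40 participants (20 per group) was chosen based on feasibility". In addition, if the two diagnosis groups happen to differ in how many received oxytocin first, that trial's estimate is displaced.

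**Working it through.** **Inputs.** From section VI: 20 per group; "all models will employ a two-sided alpha=0.05 to determine significance"; 81% power at f=0.23 for the between-group contrast of the oxytocin-minus-placebo difference. Not in the documents and therefore assumed: single-visit SD 1; within-person correlation rho 0.5 or 0.7 (0.3 also in step 2); period shift p of 0 to 0.8 SD, additive and equal in both diagnosis groups.

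**Step 1: the plan's own figure.** For a 2-group by 2-measurement interaction,

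lambda = f² × N × m / (1 − rho) = 0.0529 × 40 × 2 / 0.5 = 8.464, with 1 and 38 df.

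Power is 80.9%, which matches the stated 81%. The correlation of 0.5 is inferred, because it is the value that gives 81%. The implied effect is 4f = 0.92 single-visit SD. At rho 0.5 the difference has SD √(2 × 0.5) = 1, so the effect is also 0.92 SD of the difference. The calculation allows for no period shift.

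**Step 2: residual variance of the planned regression, orders balanced within diagnosis.**

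- Without order: 1 + p²/4 − (rho − p²/4)² / (1 + p²/4)
- With order: 1 − rho²

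At p = 0.5, p²/4 = 0.0625.

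- rho 0.5: 1.0625 − 0.4375²/1.0625 = 0.882, against 0.750. The ratio is 1.176, so the residual SD is 8.5% larger and 40 participants are worth 40/1.176 = 34.
- rho 0.7: 1.0625 − 0.6375²/1.0625 = 0.680, against 0.510. The ratio is 1.333, so 40 are worth 30.
- rho 0.3: 1.0625 − 0.2375²/1.0625 = 1.009, against 0.910. The ratio is 1.109, so 40 are worth 36.

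**Step 3: simulated power of the Hypothesis 1b regression.** 40,000 trials per setting, simple randomisation of order; power without v with the order term. At rho 0.7 the effect can be read in two ways: 0.92 single-visit SD, or 0.92 SD of the difference, which is 0.92 × √0.6 = 0.71 single-visit SD.

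| Period shift | rho 0.5, effect 0.92 | rho 0.7, effect 0.92 | rho 0.7, effect 0.71 |
|---|---|---|---|
| 0 | 89.5% v 88.6% | not run | 86.2% v 85.2% |
| 0.2 | 88.7% v 88.7% | 96.8% v 97.2% | 84.2% v 85.4% |
| 0.3 | 87.9% v 88.9% | not run | 81.5% v 85.0% |
| 0.5 | 84.3% v 88.7% | 92.3% v 97.2% | 74.5% v 84.7% |
| 0.8 | 77.4% v 88.7% | 83.4% v 96.9% | 62.3% v 84.9% |

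The table omits the medication covariate. Adding it, with an assumed 10 of 20 BDD and 2 of 20 control users and no medication effect, gives at p = 0.5: 76.4% v 81.6% (rho 0.5) and 65.4% v 76.4% (rho 0.7, effect 0.71).

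**Step 4: validity, no true effect, p = 0.5, rho 0.5.** Averaged over random orders, with no placebo gap between groups, bias is −0.003 SD and type I error 5.0%. Conditional on the numbers receiving oxytocin second in the two groups:

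- 12 v 8 of 20: the estimate shifts 0.14 SD; type I error 5.6%.
- 13 v 7 of 20: the estimate shifts 0.21 SD; type I error 8.7%.
- With the order term: shift below 0.003 SD and error 4.8% to 5.1%.

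If order is simply randomised (two independent binomials, n = 20, probability 0.5), a gap of 4 or more has probability 27%, and of 6 or more 8%.

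**Step 5: a placebo gap.** If BDD scores 0.8 SD lower on both sprays (rho 0.5), the placebo-adjusted estimate is already −0.40 SD with no period shift. At p = 0.5 it becomes −0.47 SD, and order restores −0.40. The remaining −0.40 is a separate problem.

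**Step 6: Hypothesis 1a, gap 0.92 SD.** Without v with order: 80.4% v 79.6% (p = 0.2), 78.8% v 80.1% (0.5), 74.6% v 79.7% (0.8).

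**The case against.** The strongest reply is that the harm depends on a quantity the documents do not give. No feedback on correct answers is described, and the visits are separated by a one-week washout. At rho 0.5 a shift of 0.2 SD costs nothing and 0.3 SD costs 1 point, so a material loss needs about 0.5 SD or more. Type I error is correct on average. The largest losses (10 points at 0.5 SD and 23 at 0.8 SD) come from rho 0.7 with the effect reduced to 0.71 SD. On the plan's f=0.23, read as 0.92 single-visit SD, the loss at 0.5 SD is 4 to 5 points. Only the Emotion Recognition total has a clear argument for a shift, and blocking adds only about 1 point once order is in the model.

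Most of this stands as a limit on size. The 4 to 5 points should be the lead figure, and the imbalance probabilities assume simple randomisation, which the plan does not specify. None of it supplies a reason to leave the term out. Order is already randomised and recorded, the cost if there is no shift is about 1 point, and the shift cannot be ruled out beforehand. Adding the medication covariate lowers all the power levels but leaves a gap of about 5 points at 0.5 SD and rho 0.5.

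**Conclusion.** The concern holds. The omission is plain in section VI, and no other feature of the design covers it. On the effect implied by f=0.23, the Hypothesis 1b regression loses nothing at a shift of 0.2 SD (under half a point at rho 0.7), about 4 to 5 points of power at 0.5 SD, and 11 to 14 points at 0.8 SD. The loss at 0.5 SD rises to about 10 points if the correlation is 0.7 and the effect is 0.71 single-visit SD. The test is not biased by the omission on average when the groups have equal placebo means, but a trial with an uneven order split carries a displaced estimate. All of this rests on an assumed additive shift common to both groups. The omission itself is certain; the size of the harm is not. The case is best made for the Emotion Recognition total, and the effect on Hypotheses 1a and 2a is small. The change should be made because it is cheap and has to be pre-specified to be credible.

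**What to change.** 1. Add randomised spray order (oxytocin first or second) as a covariate in the Hypothesis 1b and 2b regressions, keeping the placebo score. Each participant contributes one row, so this single indicator also carries period.
2. Use the same variable, as placebo visit number, in the Hypothesis 1a and 2a regressions, where the gain is small.
3. Have the pharmacy block-randomise order within each diagnosis group, but only together with the order term. Blocking alone makes the estimate less variable while the order variance stays in the residual, so the test turns conservative: at a shift of 0.5 SD, type I error is 3.5% at rho 0.5 and 2.5% at rho 0.7. With the term, blocking raises power from 88.7% to 89.8% and from 84.7% to 86.0%, respectively.
4. State in the SAP that one order term assumes the same shift in both diagnosis groups. A shift that differs by diagnosis would need an order-by-diagnosis term.

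The cost is one degree of freedom (about 1 point of power under simple randomisation if there is no shift), a sentence or two in section VI, and two pharmacy lists instead of one. No new data are collected. If order lists have already been issued, the covariate alone still works.

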Given that oxytocin is involved in the regulation of a variety of dimensions of social cognition and behavior, including emotion recognition and social information processing, there are direct implications regarding its role in the development of such deficits among individuals BDD in particular. Individuals with BDD display deficits in social cognition, as they are convinced that their appearance is flawed, and that people may be staring and laughing at their physical flaws. Experiments have shown that BDD is associated with selective attentional biases to imagined flaws in one's own face and to corresponding regions in unfamiliar others' faces (e.g., Grochowski, Kleim, & Heinrichs, 2012). Moreover, research has shown that individuals with BDD incorrectly interpret faces showing neutral emotional expressions as contemptuous and angry (Buhlmann, Etcoff, & Wilhelm, 2006). Despite these obvious problems with regard to social cognition, no studies have yet examined the effect of oxytocin in BDD. The current study therefore aims to investigate the effect of oxytocin administration on modifying core social cognitive impairments associated with BDD. This study has major public health significance, given the prevalence of OC spectrum disorders and the need to investigate more parsimonious treatments.

II. Specific Aims

Primary Aim 1: To examine differential effects of oxytocin on social cognitive deficits during an emotion recognition task and trust game by diagnosis.

Hypothesis 1a: Individuals with BDD will exhibit poor performance on the emotion recognition task and trust game, compared to healthy controls.

Hypothesis 1b: The effects of oxytocin vs. placebo on the emotion recognition task and trust game will be greater for individuals with BDD than for healthy controls.

Secondary Aim 2: To examine the effect of oxytocin on cognitive biases (attentional and interpretive biases) associated with BDD.

Hypothesis 2a: Individuals with BDD (compared to healthy controls) will exhibit the following cognitive biases: attentional bias (difficulty disengaging from threat cues, as measured by a spatial cueing paradigm), and negative interpretive bias (as measured by an interpretation questionnaire).

Hypothesis 2b: For individuals with BDD (compared to healthy controls), oxytocin will attenuate these biases compared to placebo.

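### The planned analysis never estimates oxytocin against placebo within participants, so the overall aim, Secondary Aim 2 and part of Hypothesis 2b go unanswered

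*Combined protocol and SAP*

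**What the plan says.** Section I gives the purpose: "The current study therefore aims to investigate the effect of oxytocin administration on modifying core social cognitive impairments associated with BDD". Section II then sets three relevant targets:

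- Primary Aim 1: "To examine differential effects of oxytocin on social cognitive deficits during an emotion recognition task and trust game by diagnosis". Hypothesis 1b accordingly predicts a larger oxytocin effect in BDD than in controls.
- Secondary Aim 2: "To examine the effect of oxytocin on cognitive biases (attentional and interpretive biases) associated with BDD".
- Hypothesis 2b: "For individuals with BDD (compared to healthy controls), oxytocin will attenuate these biases compared to placebo".

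Under Treatment Assignment Procedures (Section IV), "all participants will receive an oxytocin and placebo nasal spray at two separate visits", and "The MGH Research Pharmacy will randomize the order of nasal sprays that will be given to participants". This applies to both diagnostic groups.

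Section VI states that the BDD versus healthy control comparison is the effect of interest in all models. Hypotheses 1a and 2a regress the placebo score on diagnosis. For Hypothesis 1b, "we will regress oxytocin outcome scores against diagnosis, and will control for the placebo outcome score", and Hypothesis 2b mirrors this. The exploratory models test moderator by diagnosis. Concomitant medication is a covariate throughout. The power statement concerns BDD versus controls on the mean within-subject difference.

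**The concern.** Diagnosis is not randomised; the order of oxytocin and placebo is. Yet no planned model has a drug term, and Section VI contains no oxytocin-minus-placebo estimate, interval or test in BDD, in controls or pooled.

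A contrast between groups shows that the groups differ. It does not show which group moved, or in which direction. A significant diagnosis term can arise because controls worsened while BDD participants stayed the same. A non-significant one can arise because both groups benefited equally. In either case the question in Section I and Secondary Aim 2, whether oxytocin changes anything in BDD, has no planned answer. Any within-BDD comparison reported later would be post hoc.

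**Working it through.** **1. What each planned model tests, against what is asked**

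| Target (Sections I and II) | Asks for | Planned term (Section VI) | Answered? |
|---|---|---|---|
| Overall aim | oxytocin effect in BDD | none | no |
| Primary Aim 1, H1b | difference in effect by diagnosis | diagnosis, adjusted for placebo score | contrast of the right kind |
| Secondary Aim 2 | oxytocin effect on BDD biases | diagnosis, adjusted for placebo score | no |
| H2b | attenuation against placebo in BDD, relative to controls | diagnosis, adjusted for placebo score | the group part only |

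**2. The plan's own power figure**

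Inputs from Power and Sample Size: N = 40 (20 per group), f = 0.23, two-sided alpha 0.05, stated power 81%. The documents give no within-person correlation; ρ = 0.5 is assumed.

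For a group-by-drug interaction with m = 2 measurements, λ = f²·N·m/(1 − ρ) = 0.0529 × 40 × 2 / 0.5 = 8.464. With 1 and 38 df the power is 80.9%, so the figure reproduces. At ρ = 0.3 it is 66.9%, and at ρ = 0.7 it is 95.5%.

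The implied group difference, in SDs of the difference scores, is √(2λ/20) = √0.8464 = 0.92. The 81% is therefore power for a difference between groups. It says nothing about a drug effect within BDD.

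**3. Power of the missing test**

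For a paired t-test in 20 BDD participants, the noncentrality is d_z·√20 with 19 df, where d_z is the mean difference divided by the SD of the differences. Power is 25% at d_z = 0.3, 56% at 0.5, 80% at 0.66 and 92% at 0.8. Losing one further df to a period term leaves the 80% point at 0.66. A two-group comparison of difference scores needs 0.91 for 80% power.

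**4. How the planned model behaves**

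The model is oxytocin score on diagnosis, adjusted for placebo score, with 20 per group and two-sided alpha 0.05. The medication covariate is left out. ρ, the effects and the placebo gaps are assumptions, because the documents give none. Higher scores are taken as better. With ρ = 0.5 the SD of the difference is √(2 × (1 − 0.5)) = 1 score SD, so effects read the same on either scale.

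Let e_B and e_C be the oxytocin effects in BDD and controls, and g the BDD-minus-control gap on placebo. The planned coefficient has expectation (e_B − e_C) + g·(1 − ρ). Rejection rates come from simulation with at least 20,000 runs per scenario, except the paired 92%, which is the exact power from step 3.

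| g | e_B | e_C | Expected coefficient | Planned test significant | Paired test in BDD significant |
|---|---|---|---|---|---|
| 0 | 0 | −0.9 | 0.9 | about 88% | 5% |
| −0.8 | 0 | −0.9 | 0.9 − 0.4 = 0.5 | about 37% | 5% |
| 0 | 0.8 | 0.8 | 0 | 5% | 92% |
| −0.8 | 0.8 | 0.8 | 0 − 0.4 = −0.4 | about 26% | 92% |
| −0.8 | 0.4 | 0 | 0.4 − 0.4 = 0 | about 5% | 40% |

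In the last row the benefit is confined to BDD and the placebo deficit is in the direction Hypothesis 1a predicts, yet the planned coefficient averages about zero. At ρ = 0.3 its expectation would be 0.4 − 0.8 × 0.7 = −0.16, and at ρ = 0.7 it would be 0.4 − 0.8 × 0.3 = 0.16.

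Across ρ = 0.3 and 0.7, with effects held in SDs of the difference and the gap in score SDs, the first row gives 92% and 85%, the second 31% and 44%, and the fourth 38% and 16%. The third stays at about 5%.

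**The case against.** The strongest reply is that the hypotheses are largely between-group. Primary Aim 1 and Hypothesis 1b ask for a differential effect by diagnosis, and Hypothesis 2b includes the comparison with controls. This stands: a diagnosis contrast is the right kind of test for Aim 1, and there the within-BDD estimate aids interpretation. A reader might infer that the primary hypothesis goes untested; the documents do not support that.

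A reader might also infer that the trial cannot say whether oxytocin works in BDD. That goes too far. Both scores are collected for every participant, so the silence is in the written analysis and not in the data. Nor is the randomised contrast confined to BDD, since spray order is randomised in controls as well. The power statement does bring the within-person difference into the group comparison, so it is not ignored altogether. The documents set no rule for wording conclusions, so misreading is a risk and not a stated intention.

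The scenarios can be challenged too. Controls worsening by 0.9 SD is an extreme case, and with a placebo gap of 0.8 SD the planned test is significant about 37% of the time, not 88%. Equal benefit in both groups yields a null diagnosis term only when the groups do not differ on placebo. These points change the size of the illustration. They do not supply the missing estimate.

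**Conclusion.** The concern holds in limited form. Section VI contains no oxytocin-versus-placebo estimate within participants in either group. The planned diagnosis contrast therefore serves Primary Aim 1 and Hypothesis 1b, but leaves the overall aim, Secondary Aim 2 and the placebo-comparison part of Hypothesis 2b without an analysis.

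That finding rests on the text alone. Its practical size depends on the assumed correlation, effects and placebo gaps. At ρ = 0.5 the planned test and a paired test in BDD can disagree sharply in both directions: about 88% against 5%, and 5% against 92%. A benefit confined to BDD can also be missed, at about 5% against 40%. The change should be made; it does not overturn the test of the primary hypothesis.

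**What to change.** In Section VI, for each primary and secondary outcome, pre-specify the oxytocin-minus-placebo contrast within BDD, with estimate, 95% CI and p-value, adjusted for period. Give the same contrast in controls as supportive. One mixed model with drug, diagnosis, drug by diagnosis and period would provide both. Keep the diagnosis comparison as the test of differential effect.

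Add a rule for conclusions: state that oxytocin improves or attenuates an outcome in BDD only if the within-BDD 95% CI excludes zero in the beneficial direction. Otherwise report only an estimate or a group difference. Requiring merely a favourable direction is too weak. With no effect in BDD and controls 0.9 SD worse, about 60% of significant positive group results on difference scores would pass that rule, against about 3% if the CI must exclude zero.

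The cost is a few lines of text and two contrasts for each of the four named outcomes, eight in all, whose confirmatory or supportive status must be stated. No new data or participants are needed. The price is that a significant diagnosis term alone supports a narrower claim, and with 20 BDD participants the paired contrast has 80% power only from 0.66 SD of the difference.
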